3.2 Ipilimumab

Full background drug information and description please reference Ipilimumab Investigator's Brochure (V18 dated 10MAR2015).

3.2.1 Description

Ipilimumab is a recombinant, human mAb that binds to the cytotoxic T-lymphocyte-associated antigen 4 (CTLA-4). Ipilimumab is an IgG1 kappa immunoglobulin with an approximate molecular weight of 148 kDa. Ipilimumab is produced in mammalian (Chinese hamster ovary) cell culture.

3.2.2 Mechanism of action

Amendment9 09NOV2021 Page 21 of 77

CTLA-4 is a negative regulator of T-cell activity. Ipilimumab is a mAb that binds to CTLA-4 and blocks the interaction of CTLA-4 with its ligands, CD80/CD86. Blockade of CTLA-4 has been shown to augment T-cell activation and proliferation, including the activation and proliferation of tumor infiltrating T-effector cells. Inhibition of CTLA-4 signaling can also reduce T-regulatory cell function, which may contribute to a general increase in T cell responsiveness, including the anti-tumor immune response⁹.

3.2.3 Pharmacokinetics

The pharmacokinetics (PK) of ipilimumab was studied in 785 patients with unresectable or metastatic melanoma who received doses of 0.3, 3, or 10 mg/kg once every 3 weeks for 4 doses. The PK of ipilimumab is linear in the dose range of 0.3 to 10 mg/kg. Following administration of ipilimumab every 3 weeks, the systemic accumulation was 1.5-fold or less. Steady-state concentrations of ipilimumab were reached by the third dose; the mean Cmin at steady state was 19.4 mcg/mL at 3 mg/kg and 58.1 mcg/mL at 10 mg/kg every 3 weeks. The mean value (percent coefficient of variation) based on population PK analysis for the terminal half-life (t1/2) was 15.4 days (34%) and for clearance (CL) was 16.8 mL/h (38%).

The effects of various covariates on the PK of ipilimumab were assessed in population PK analyses. The CL of ipilimumab increased with increasing body weight supporting the recommended body weight (mg/kg) based dosing. The following factors had no clinically important effect on the CL of ipilimumab: age (range: 23 to 88 years), sex, performance status, renal impairment, mild hepatic impairment, previous cancer therapy, and baseline lactate dehydrogenase (LDH) levels. The effect of race was not examined due to limited data available in non-Caucasian ethnic groups.

3.2.4 Non-clinical toxicology

The carcinogenic potential of ipilimumab has not been evaluated in long-term animal studies, and the genotoxic potential of ipilimumab has not been evaluated. Fertility studies have not been performed with ipilimumab.

3.2.5 Adverse events

More than 12,700 subjects with several cancer types have received ipilimumab in completed and ongoing studies, as well as a compassionate use program. The focus of the clinical program is in melanoma, prostate cancer, and lung cancer, with advanced melanoma being the most comprehensively studied indication. Ipilimumab is being investigated both as monotherapy and in combination with other modalities such as chemotherapy, radiation therapy, and other immunotherapies. Phase 3 programs are ongoing in melanoma, prostate cancer, and lung cancer.

The unique immune based mechanism of action is also reflected in the safety profile. The most common treatment related adverse events (AEs) are inflammatory in nature, consistent with the mechanism of action of ipilimumab, and generally medically manageable with topical or systemic immunosuppressants. Such immunological safety events are described as immune-related AEs (irAEs). The irAEs are described as AEs of unknown etiology that were consistent with an immune phenomenon, and were considered causally related to drug exposure by investigators. The irAEs primarily involve the gastrointestinal tract and the skin. Immune-related AEs in the liver were also observed, particularly in subjects receiving 10 mg/kg. Endocrinopathy and neuropathy were important irAEs observed less frequently.

4.0 PATIENT ELIGIBILITY

4.1 Inclusion Criteria

In order to be eligible for participation in this trial, the subject must meet the following inclusion criteria:

- 1. Voluntary signed and dated IRB/IEC approved written informed consent form in accordance with regulatory and local guidelines.
- 2. Be 18 years or older and 80 years or younger on the day of signing consent
- 3. Have a confirmed diagnosis of:
 - o (GROUP A) De novo diffuse large B cell lymphoma that fails to achieve a PET negative complete response to primary rituximab and anthracycline based multiagent chemotherapy and at least maintains stable disease after salvage chemotherapy or present double/triple hit features defined by overexpression by standard immunohistochemistry of c-MYC plus BCL2 and/or BCL6 or presence of chromosomal translocations as detected by break-apart FISH involving IGH/MYC plus IGH/BCL2 and/or IGH/BCL6 and who only received standard chemoimmunotherapy with rituximab, cyclophosphamide, vincristine and prednisone (R-CHOP) for induction and present at least stable disease after consolidation or salvage chemotherapy. Stable disease (SD) for lymphoma is defined in Appendix B: Lugano Classification for Response Assessment of Non-Hodgkin Lymphoma.
 - O (GROUP B) Recurrent high-risk diffuse large B cell lymphoma defined as relapsing within one year of completion of rituximab and anthracycline based multi-agent chemotherapy or a sAAIPI (second-line age-adjusted International Prognostic Index) intermediate or high at relapse or acquisition of double/triple hit features upon relapse (as defined in group A) and at least stable disease after salvage chemotherapy. Patients with an initial diagnosis of low-grade/indolent non-Hodgkin lymphoma (i.e. follicular, marginal zone) who present relapse with histologic transformation to diffuse large B cell lymphoma (confirmed by biopsy) and meet the definition for high-risk as presented above, are also eligible.
 - O (GROUP C) De novo high-risk T cell lymphoma with at least stable disease after primary therapy. High risk T cell lymphoma is defined as Stage III or IV disease at presentation and/or failure to achieve CR after frontline chemotherapy. Patients with ALK-positive ALCL will be excluded from the trial. Patients with ALK-negative ALCL in complete response will be excluded from the trial.
 - (GROUP D) Recurrent T cell lymphoma with at least stable disease after salvage therapy. Patients with ALK-positive ALCL will be excluded from the trial.
- 4. Be deemed eligible for an autologous stem cell transplantation according to the institutional guidelines of the Blood and Marrow Transplantation Program at John Theurer Cancer Center at Hackensack University Medical Center
- 5. Have an ECOG performance status of 2 or lower
- 6. Women of childbearing potential (WOCBP) must use appropriate method(s) of contraception. WOCBP should use an adequate method to avoid pregnancy for 23 weeks

- (30 days plus the time required for nivolumab to undergo five half-lives) after the last dose of investigational drug.
- 7. Women of childbearing potential (WOCBP) must have a negative serum or urine pregnancy test (minimum sensitivity 25 IU/L or equivalent units of HCG) within 24 hours prior to the start of nivolumab. If the urine test is positive or cannot be confirmed as negative, a serum pregnancy test will be required. Female subjects of childbearing potential should agree to ongoing pregnancy testing, to be performed prior to each dosing of ipilimumab and nivolumab. See Note below for definition of WOCBP.
- 8. Women must not be breastfeeding.
- 9. Men who are sexually active with WOCBP must use any contraceptive method with a failure rate of less than 1% per year. Men receiving nivolumab, and who are sexually active with WOCBP will be instructed to adhere to contraception for a period of 31 weeks after the last dose of investigational product, even if they have had a vasectomy. Women who are not of childbearing potential (ie, who are postmenopausal or surgically sterile as well as azoospermic men do not require contraception). See Note below for definition of WOCBP.
- 10. Females of childbearing potential must be willing to use two methods of birth control or be surgically sterile, or abstain from heterosexual activity for the course of the study through 120 days after the last dose of study medication. Subjects of childbearing potential are those who have not been surgically sterilized or have not been free from menses for > 2 years. See Note below for definition of WOCBP.
- 11. Allowable transplant preparative regimens are the following:
 - For non-Hodgkin lymphoma groups (A, B,C,D) BEAM: carmustine 300 mg/m2 day
 -6, etoposide 200 mg/m2 and cytarabine 200 mg/m2 days -5 to -2, melphalan 140 mg/m2 day -1
 - o For Myeloma groups (E and F) Melphalan 200 mg/m2 day -1

NOTE: Women of childbearing potential is defined as any female who has experienced menarche and who has not undergone surgical sterilization (hysterectomy or bilateral oophorectomy) or who is not postmenopausal. Menopause is defined clinically as 12 months of amenorrhea in a woman over 45 in the absence of other biological or physiological causes. In addition, women under the age of 55 must have a documented serum follicle stimulating hormone (FSH) level less than 40 mIU/mL.

Women of childbearing potential (WOCBP) receiving nivolumab will be instructed to adhere to contraception for a period of 23 weeks after the last dose of investigational product. Men receiving nivolumab and who are sexually active with WOCBP will be instructed to adhere to contraception for a period of 31 weeks after the last dose of investigational product. These durations have been calculated using the upper limit of the half-life for nivolumab (25 days) and are based on the protocol requirement that WOCBP use contraception for 5 half-lives plus 30 days and men who are sexually active with WOCBP use contraception for 5 half-lives plus 90 days.

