- 10. Has known history of, or any evidence of active, non-infectious pneumonitis.
- 11. Has an active infection requiring intravenous systemic therapy.
- 12. Has a history or current evidence of any condition, therapy, or laboratory abnormality that might confound the results of the trial, interfere with the subject's participation for the full duration of the trial, or is not in the best interest of the subject to participate, in the opinion of the treating investigator.
- 13. Has known psychiatric or substance abuse disorders that would interfere with cooperation with the requirements of the trial.
- 14. Is pregnant or breastfeeding, or expecting to conceive or father children within the projected duration of the trial, starting with the prescreening or screening visit through 23 weeks for females and 31 weeks for males after the last dose of trial treatment.
- 15. Has received prior therapy with an anti-PD-1, anti-PD-L1, anti-PD-L2 agent, anti-CTLA-4 antibody, or any other antibody or drug specifically targeting T-cell costimulation or immune checkpoint pathways.
- 16. Has a known history of Human Immunodeficiency Virus (HIV) (HIV 1/2 antibodies) or known acquired immunodeficiency syndrome (AIDS).
- 17. Has positive test for Hepatitis B (e.g., HBsAg reactive) or Hepatitis C (e.g., HCV RNA [qualitative] is detected) indicating acute or chronic infection, as tested for transplant.
- 18. Has received a live vaccine within 30 days of planned start of study therapy.

NOTE: Patients who received steroids for engraftment syndrome may initiate treatment with ipilimumab and nivolumab once steroids have been tapered off and diarrhea and/or rash are grade I or better, without the need

Amendment9 09NOV2021 Page 7 of 77

	for a steroid washout period. Initial dosing may be delayed up to day 28 post-transplantation to allow for completion of steroid taper.		
Combined Check Point Inhibition	Start 14 to 21 days after stem cell infusion if ANC>800 (off growth factors for at least 3 days) and Platelets>20,000 without transfusion		
	Delay initiation until ANC>800 (off growth factors for at least 3 days) and Platelets>20,000 without transfusion up to 28 days after stem cell infusion. The first day of combined checkpoint inhibitor therapy will be considered Week 1, day 1 for the purposes of this protocol.		
	Post ASCT therapy may be delayed up to 28 days after stem cell infusion if deemed appropriate by the investigator.		

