- 10. Has known history of, or any evidence of active, non-infectious pneumonitis.
- 11. Has an active infection requiring intravenous systemic therapy.
- 12. Has a history or current evidence of any condition, therapy, or laboratory abnormality that might confound the results of the trial, interfere with the subject's participation for the full

Amendment9 09NOV2021 Page 25 of 77

- duration of the trial, or is not in the best interest of the subject to participate, in the opinion of the treating investigator.
- 13. Has known psychiatric or substance abuse disorders that would interfere with cooperation with the requirements of the trial.
- 14. Is pregnant or breastfeeding, or expecting to conceive or father children within the projected duration of the trial, starting with the pre-screening or screening visit through 23 weeks for females and 31 weeks for males after the last dose of trial treatment.
- 15. Has received prior therapy with an anti-PD-1, anti-PD-L1, anti-PD-L2 agent, anti-CTLA-4 antibody, or any other antibody or drug specifically targeting T-cell costimulation or immune checkpoint pathways.
- 16. Has a known history of Human Immunodeficiency Virus (HIV) (HIV 1/2 antibodies) or known acquired immunodeficiency syndrome (AIDS).
- 17. Has positive test for Hepatitis B (e.g., HBsAg reactive) or Hepatitis C (e.g., HCV RNA [qualitative] is detected) indicating acute or chronic infection, as tested for transplant.
- 18. Has received a live vaccine within 30 days of planned start of study therapy.

NOTE: Patients who received steroids for engraftment syndrome may initiate treatment with ipilimumab and nivolumab once steroids have been tapered off and diarrhea and/or rash are grade I or better, without the need for a steroid washout period. Initial dosing may be delayed up to day 28 post-transplantation to allow for completion of steroid taper.

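### The FSH limit used to confirm menopause in women under 55 points the wrong way in the Note defining childbearing potential (minor)

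*Combined protocol and SAP*

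**What the plan says.** The Note after the inclusion criteria in section 4.1, repeated in the synopsis, treats a woman past menarche as of childbearing potential (WOCBP) if she is someone "who has not undergone surgical sterilization (hysterectomy or bilateral oophorectomy) or who is not postmenopausal". It then gives the clinical definition: "Menopause is defined clinically as 12 months of amenorrhea in a woman over 45 in the absence of other biological or physiological causes". The next sentence opens as an addition to that definition and says that "women under the age of 55 must have a documented serum follicle stimulating hormone (FSH) level less than 40 mIU/mL".

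Several provisions depend on this classification:

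- Item 6: "WOCBP should use an adequate method to avoid pregnancy for 23 weeks", counted from the last dose.
- Item 7: "Female subjects of childbearing potential should agree to ongoing pregnancy testing, to be performed prior to each dosing of ipilimumab and nivolumab". It also requires a negative test within 24 hours before nivolumab starts, and it refers to the Note.
- Item 9: "Women who are not of childbearing potential (ie, who are postmenopausal or surgically sterile as well as azoospermic men do not require contraception".
- Appendix D, footnote c, limits the pregnancy-test row to women of childbearing potential.
- Item 10 has its own definition (not sterilized, or not free of menses for more than 2 years). It requires two contraceptive methods, or abstinence, through 120 days after the last dose, and it also refers to the Note.

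Exclusion 14 applies whatever the classification. It covers anyone who "Is pregnant or breastfeeding, or expecting to conceive or father children within the projected duration of the trial", from "screening visit through 23 weeks for females and 31 weeks for males after the last dose of trial treatment".

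**The concern.** The FSH value is meant to confirm menopause in women young enough for amenorrhea alone to leave doubt. FSH rises at menopause. This is basic physiology, and the documents give no reference range. A value below 40 therefore argues against menopause, and a value well above it supports menopause. As worded, the confirming test passes the women it should hold and holds the women it should pass.

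The limit is spelled out in words and is identical in both places, so it is not a symbol lost in reading the PDF. No other part of the protocol mentions FSH or corrects it. At stake are pregnancy testing during treatment with two checkpoint inhibitors and contraception during and after it.

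**Working it through.** **Inputs.** Section 4.1 Note: half-life 25 days; 5 half-lives plus 30 days for women and plus 90 days for men. Section 5.3: 12 dosing days (weeks 1, 4, 7, 10, 12, 14, 16, 18, 20, 22, 24, 26). Appendix D: pregnancy test marked at screening, dosing days, end of treatment and the 30-day safety visit. Item 10: 120 days.

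**The plan's own figure.** Women: 5 × 25 + 30 = 155 days; 155 / 7 = 22.1, rounded up to 23 weeks, or 23 × 7 = 161 days. Men: 5 × 25 + 90 = 215 days; 215 / 7 = 30.7, rounded up to 31 weeks. Both reproduce.

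**Scheduled pregnancy tests.** With d dosing days: 1 (screening) + d + 1 (end of treatment) + 1 (30-day visit) = 3 + d. For d = 1 this is 4. For d = 12 it is 15, the maximum. The week 1 test can serve as the test within 24 hours before nivolumab, so that requirement adds none.

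**Item 10 against item 6.** 161 − 120 = 41 days (155 − 120 = 35 against the unrounded figure).

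**Who changes class.** The conditions are age over 45 and under 55 (46 to 54 in whole years), at least 12 months' amenorrhea and no other cause. The Note's *or* is read as *and*.

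| Documented FSH | As written | Inequality turned |
|---|---|---|
| below 40 | postmenopausal | WOCBP |
| exactly 40 | WOCBP | WOCBP |
| above 40 | WOCBP | postmenopausal |

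No other woman changes class. A woman under 55 with no documented FSH is not exempted under either wording.

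**What a woman with FSH below 40 loses, on that reading.**

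- 12 to 24 months from last menses: the Note drops the tests and the 23-week rule. Item 10, by its own definition, keeps her under contraception to 120 days. Because item 7 speaks of female subjects of childbearing potential, testing arguably continues too, although item 7 defines the term by the Note.
- More than 24 months from last menses: if item 10's *or* is also read as *and*, she meets neither definition. No contraception rule then applies during dosing or in the 161 days after the last dose.

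**Reverse error.** With FSH of 40 or more, the same woman keeps up to 15 tests and 161 days of contraception after the last dose. Where FSH is above 40, the Note is evidently meant to spare her these, although item 10 would still hold her to 120 days if she is 12 to 24 months from last menses.

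**The case against.** The strongest reply is that the harm needs edited text. Taken literally, the Note's *or* keeps every unsterilized woman past menarche as WOCBP whatever her FSH, and nobody loses a test. A site that mends the *or* by common sense may mend the FSH limit as well. This stands as a limit on the harm. It does not rescue the wording: the literal *or* would empty item 9's exemption for postmenopausal women, so *and* is the workable reading, and the FSH sentence is wrong on either.

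A reader might infer that every released woman has no contraception rule at all. The documents do not support that. Section 4.1 says that subjects must meet the listed criteria, so item 10 is not optional for sites. Its cross-reference to the Note leaves some ambiguity, but its own definition covers women 12 to 24 months from last menses.

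A reader might also infer that a pregnant woman could properly be treated. Exclusion 14 bars a known pregnancy whatever the label, and section 5.2 requires eligibility to be confirmed again before Week 1 Day 1. Neither names a pregnancy test, so they reduce the gap without closing it.

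Finally, the group is narrow. FSH is on neither the section 6.1 screening list nor the flowchart. These patients have had chemotherapy, which an investigator may count as another cause of amenorrhea. That is a fair reason for a low severity rating.

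**Conclusion.** Wrong as written; minor severity. The reversed limit is certain from the text, given only that FSH rises at menopause. The consequence is conditional. With the Note's *or* read as *and*, a woman aged 46 to 54 who meets the clinical definition and has FSH below 40 can lose between 4 and 15 scheduled tests and the 23-week rule. Complete loss of a contraception rule is confined to women more than 24 months from last menses and needs a second reading of *or* as *and*, in item 10. The figure of 15 is a ceiling for a woman who attends all 12 dosing days, not a typical loss. The documents do not say how many women are affected, and the number is probably small. No endpoint, sample size, stopping rule or analysis is touched.

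**What to change.** In the Note, in both the synopsis and section 4.1:

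1. Change less than 40 mIU/mL to greater than 40 mIU/mL, with the sponsor confirming the cut-off.
2. Reword the definition so that a woman is of childbearing potential if she is past menarche, not surgically sterilized **and** not postmenopausal.

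Then check the charts of enrolled women under 55 who were classed as not of childbearing potential.

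As a separate repair that adds no weight to this point, change item 10's 120 days to 23 weeks to match item 6. Keep item 10's 2-year interval, because replacing it with the Note's 12 months would remove a protection for women 12 to 24 months from last menses.

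The cost is a short amendment and a chart check, with no extra patients. The 41 days added to item 10 are already required of WOCBP by item 6.

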4.2 Exclusion Criteria

The subject must be excluded from participating in the trial if the subject meets ANY of the following exclusion criteria:

1. Has known active central nervous system (CNS) metastases and/or carcinomatous meningitis. Subjects with previously treated brain metastases may participate provided they are stable (without evidence of progression by imaging for at least four weeks prior to the first dose of trial treatment and any neurologic symptoms have returned to baseline),

have no evidence of new or enlarging brain metastases, and are not using steroids for at least 7 days prior to trial treatment. There must also be no requirement for immunosuppressive doses of systemic corticosteroids (> 10 mg/day prednisone equivalents) for at least 2 weeks prior to study drug administration. This exception does not include carcinomatous meningitis, which is excluded regardless of clinical stability. Note: Subjects are permitted to use topical, ocular, intra-articular, intranasal, and inhalational corticosteroids (with minimal systemic absorption). Physiologic replacement doses of systemic corticosteroids are permitted, even if > 10 mg/day prednisone equivalents. A brief course of corticosteroids for prophylaxis (eg, contrast dye allergy) or for treatment of non-autoimmune conditions (eg, delayed-type hypersensitivity reaction caused by contact allergen) is permitted.

- 2. Is unable or unwilling to sign informed consent.
- 3. Has an active, known, or suspected autoimmune disease. Subjects are permitted to enroll if they have vitiligo, type I diabetes mellitus, residual hypothyroidism due to autoimmune condition only requiring hormone replacement, psoriasis not requiring systemic treatment, or conditions not expected to recur in the absence of an external trigger
- 4. Patients should be excluded if they have a condition requiring systemic treatment with either corticosteroids (> 10 mg daily prednisone equivalents) or other immunosuppressive medications within 14 days of study drug administration. Inhaled or topical steroids and adrenal replacement doses > 10 mg daily prednisone equivalents are permitted in the absence of active autoimmune disease. Note: Subjects are permitted to use topical, ocular, intra-articular, intranasal, and inhalational corticosteroids (with minimal systemic absorption). Physiologic replacement doses of systemic corticosteroids are permitted, even if > 10 mg/day prednisone equivalents. A brief course of corticosteroids for prophylaxis (eg, contrast dye allergy) or for treatment of non-autoimmune conditions (eg, delayed-type hypersensitivity reaction caused by contact allergen) is permitted.
- 5. As there is potential for hepatic toxicity with nivolumab or nivolumab/ipilimumab combinations, drugs with a predisposition to hepatoxicity should be used with caution in patients treated with nivolumab-containing regimen.
- 6. Has received an allogeneic stem cell transplant.
- 7. Has a history of hypersensitivity to nivolumab, ipilimumab, or any of its excipients, or severe hypersensitivity reaction to any previous monoclonal antibody.
- 8. Has had a prior anti-cancer monoclonal antibody (mAb) within 4 weeks prior to Day 1 of checkpoint inhibitor treatment administration or who has not recovered (i.e., t administration mAb) within 4 weeks prior to t dose of trial treatment. Rituximab within that period is allowed.
- 9. Has active autoimmune disease that has required systemic treatment in the past 2 years (i.e. with use of disease modifying agents, corticosteroids or immunosuppressive drugs). Replacement therapy (eg. thyroxine, insulin, or physiologic corticosteroid replacement therapy for adrenal or pituitary insufficiency, etc.) is not considered a form of systemic treatment. Note: Subjects are permitted to use topical, ocular, intra-articular, intranasal, and inhalational corticosteroids (with minimal systemic absorption). Physiologic replacement doses of systemic corticosteroids are permitted, even if > 10 mg/day prednisone equivalents. A brief course of corticosteroids for prophylaxis (eg, contrast dye allergy) or for treatment of non-autoimmune conditions (eg, delayed-type hypersensitivity reaction caused by contact allergen) is permitted.
- 10. Has known history of, or any evidence of active, non-infectious pneumonitis.
- 11. Has an active infection requiring intravenous systemic therapy.
- 12. Has a history or current evidence of any condition, therapy, or laboratory abnormality that might confound the results of the trial, interfere with the subject's participation for the full

Amendment9 09NOV2021 Page 25 of 77

- duration of the trial, or is not in the best interest of the subject to participate, in the opinion of the treating investigator.
- 13. Has known psychiatric or substance abuse disorders that would interfere with cooperation with the requirements of the trial.
- 14. Is pregnant or breastfeeding, or expecting to conceive or father children within the projected duration of the trial, starting with the pre-screening or screening visit through 23 weeks for females and 31 weeks for males after the last dose of trial treatment.
- 15. Has received prior therapy with an anti-PD-1, anti-PD-L1, anti-PD-L2 agent, anti-CTLA-4 antibody, or any other antibody or drug specifically targeting T-cell costimulation or immune checkpoint pathways.
- 16. Has a known history of Human Immunodeficiency Virus (HIV) (HIV 1/2 antibodies) or known acquired immunodeficiency syndrome (AIDS).
- 17. Has positive test for Hepatitis B (e.g., HBsAg reactive) or Hepatitis C (e.g., HCV RNA [qualitative] is detected) indicating acute or chronic infection, as tested for transplant.
- 18. Has received a live vaccine within 30 days of planned start of study therapy.

NOTE: Patients who received steroids for engraftment syndrome may initiate treatment with ipilimumab and nivolumab once steroids have been tapered off and diarrhea and/or rash are grade I or better, without the need for a steroid washout period. Initial dosing may be delayed up to day 28 post-transplantation to allow for completion of steroid taper.

